## 8.5.1.4 TSS Reduction $\geq$ 50% (TSS50)

TSS50 rate is defined as the proportion of subjects who achieved at least 50% reduction from baseline in TSS at any week during the study.

Subjects who do not have any post baseline TSS score will be treated as non-responders. Subjects with baseline TSS of 0 or without baseline TSS score will also considered as non-responders. Data after the start of post-study treatment or disease progression will not be included in the analyses.

TSS50 rate will be analyzed in the Full Analysis Set.

#### 8.5.1.5 Change in MFSAF Score

[figure not shown]
Change in average daily MFSAF score of weekly interval (7-day) for each item and TSS (except for Week 23 and Week 25) from baseline will be summarized according to the scoring approach provided in Appendix C. Data after the start of post-study treatment, disease progression will not be included in the analyses. Change in MFSAF score will be analyzed among subjects who had baseline and post-baseline MFSAF score.

#### 8.5.1.6 Post Baseline Red Blood Cell Transfusion

Post Baseline Red Blood Cell transfusion (for any reason) evaluation period is from after the first dose of study drug to earliest day of on or before the last dose of study drug + 30 days, or the start of post-study treatment.

Post baseline transfusion independent rate will be calculated as the proportion of subjects who achieved PRBC transfusion independent during the treatment period. PRBC Transfusion independent is defined as a period of at least 12 weeks (≥ 84 days) with no PRBC transfusions during the evaluation period. In addition, the rate of conversion will be calculated as proportion of subjects being post-baseline PRBC transfusion independent from baseline PRBC transfusion dependent.

The duration of PRBC transfusion independent will also be summarized for overall and by transfusion status at baseline (transfusion dependent and transfusion independent). The duration of transfusion independence is defined as the first time period that a subject received no PRBC transfusions for at least 12 weeks ( $\geq$  84 days). The descriptive

statistics (median and range) will be provided for the duration of transfusion independence.

Incidence rate of PRBC transfusion/subject/month, defined as total number of PRBC transfusion from all subjects divided by total duration of treatment from all subjects (months).

Time from first date of study treatment to the first time receiving 2 or more units of PRBC transfusion will be summarized.

Above endpoints will be analyzed in the Full Analysis Set.

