During treatment, all assessments must be performed on the day of the specified visit unless a time window is specified in the schedule of assessments (Appendix C). Refer to Section 3.6 for study visit modifications.

Subjects will continue their treatment until end of clinical benefit, unacceptable toxicity or subject meets other protocol criteria for discontinuation (whichever occurs first). All subjects will have a TCV performed when treatment is discontinued.

Response and progression will be assessed by the Investigator based on the modified International Working Group-Myeloproliferative Neoplasms Research and European Leukemia Net (IWG-MRT/ELN) and as noted in Appendix E.²⁴ Spleen volume will be assessed by an independent central review and interpretations will be transmitted to investigators, as available, and will be utilized in determining response and progression. The evaluation of fibrosis grading and reticulin staining grading may be assessed independently by a central pathologist. Independent interpretations of bone marrow samples are not planned to be transmitted to investigators. Details regarding the determination of clinical response and disease progression are provided in Appendix E.

Follow-Up

Safety Follow-Up: All subjects will have one Safety Follow-up visit approximately 30 days following TCV.

Post-Treatment Follow-Up: For subjects who discontinue study treatment for reasons other than disease progression, a Post-Treatment Follow-up visit will be performed approximately 12 weeks following TCV, then every 12 weeks thereafter to assess disease

status until criteria are met for discontinuation from study (e.g., disease progression, initiation of post-treatment cancer therapy, or subject refusal of post-treatment follow-up visits).

Once disease progression is confirmed or the subject begins a post-study treatment for MF other than the continuation of ruxolitinib (Cohorts 1a, 1b or 3), the subject will enter the Survival Follow-up phase.

Survival Follow-Up: Survival Follow-up will then be performed approximately every 6 months for up to 5 years after TCV (provided informed consent has not been withdrawn for collection of such information). Survival information (e.g., date and cause of death, details of post-treatment cancer therapies including response and progression) may be collected via telephone calls (e.g., to subject or family member), clinic visits, and/or public database searches.

5.2 **Selection of Study Population**

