Appendix C. Study Activities*

Table 6. Study Procedures – Navitoclax Alone or in Combination with Ruxolitinib

Period	Screeninga							Tı	eatmei	ıt							Follow-	Up
Week	-4 to 0	0	0	1	2	3	4	6	8	12	16	20	24	Q12 Weeks	TCV	30- Day Safety	PT ^b	Survival
Study Day	Within 28 days	1	2	8	15	22	29	43	57	85	113	141	169					
Visit Window (days)	-28	NA	NA	± 1	± 1	± 1	± 1	± 1	± 1	± 2	± 2	± 2	± 3	± 4	NA	NA	± 7	± 14
Activity				•	•				•		•	•			•			
LOCAL LABS, EXA	MS & ASSESS	MENTS																
Informed Consent	X ^c																	
Medical/Oncology History Assessment	X	X^d																
TB Testing ^e	X																	
AE/Concomitant Medication Assessment	X	X		X	X	X	X	X	X	X	X	X	X	X	X	X		
Transfusion history/status	X ^f	X		X	X	X	X	X	X	X	X	X	X	X	X	X		
Physical Exam (including skin, liver and spleen assessment) ^g	X	X		X	X	X	X	X	X	X	X	X	X	X	X	X		
12-lead ECGh	X						X								X			

EudraCT 2017-001398-17

Table 6. Study Procedures – Navitoclax Alone or in Combination with Ruxolitinib (Continued)

Period	Screeninga							Tr	eatmer	nt							Follow	-Up
Week	-4 to 0	0	0	1	2	3	4	6	8	12	16	20	24	Q12 Weeks	TCV	30- Day Safety	PT ^b	Survival
Study Day	Within 28 days	1	2	8	15	22	29	43	57	85	113	141	169					
Visit Window (days)	-28	NA	NA	± 1	± 1	± 1	± 1	± 1	± 1	± 2	± 2	± 2	± 3	± 4	NA	NA	± 7	± 14
Activity			•	•							•					•		
Vital Signs	X ⁱ	X		X	X	X	X	X	X	X	X	X	X	X	X	X		
ECOG performance status	X	X		X	X	X	X	X	X	X	X	X	X	X	X	X		
MFSAF version 4.0 ^j	X	X	X	X	X	X	X	X	X	X	X	X	X	X ^j				
EORTC QLQ-C30 ^K	X	X					X		X	X			X	X	X			
PROMIS Fatigue SF 7a ^K	X	X					X		X	X			X	X	X			
PGIC ^K							X		X	X			X	X	X			
Pregnancy Test ^l	Serum	X					X		X	X	X	X	X	X ^l	X			
Hematology ^m	X	X	X	X	X	X	X	X	X	X	X	X	X	X	X	X	X	
Chemistry	X	X ⁿ		X	X	X	X	X	X	X	X	X	X	X	X	X		
Coagulation	X																	
Lipid Parameters (fasting)	X									X								

[figure not shown]

Table 6. Study Procedures – Navitoclax Alone or in Combination with Ruxolitinib (Continued)

Period	Screeninga							Tr	eatmei	nt							Follow	-Up
Week	-4 to 0	0	0	1	2	3	4	6	8	12	16	20	24	Q12 Weeks	TCV	30- Day Safety	PT ^b	Survival
Study Day	Within 28 days	1	2	8	15	22	29	43	57	85	113	141	169					
Visit Window (days)	-28	NA	NA	± 1	± 1	± 1	± 1	± 1	± 1	± 2	± 2	± 2	± 3	± 4	NA	NA	± 7	± 14
Activity	1		•	•							•		•					
Bone Marrow Biopsy and Aspirate ^w	X									X			X	X ^w	X ^x		X ^y	
Cytogenetic Sampling ^{w,z}	X									X			X	X ^w	X ^x			
Disease Response Assessment										X			X	X^{ff}	X		X ^y	

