# 8.0 Efficacy Analyses

#### 8.1 General Considerations

The primary analysis population for primary endpoint is the Full Analysis Set. Unless otherwise specified, the secondary efficacy endpoints and exploratory efficacy endpoints will be analyzed in Full Analysis Set.

All efficacy results will be presented by cohort unless stated otherwise. For all analyses, unless otherwise specified, data collected after the cutoff date will be excluded from statistical analysis. All spleen volume related endpoints described in Section 3.0 will be based on the assessments from the central review of the radiographic images by an Independent Review Committee (IRC) as described in the protocol.

abbyie Navitoclax/ABT-263

Navitoclax/ABT-263 M16-109 – Statistical Analysis Plan Version 4.0 – 31 January 2023

All response rates and the corresponding 95% confidence interval (Cl) using the Clopper-Pearson method will be provided.

For the analyses of all time-to-event endpoints, survivorship functions will be estimated using Kaplan-Meier product-limit methodology. If reached, median time-to-event and its 95% CI will be presented.

For the analyses of all continuous endpoints, such as change from baseline in score, the scores will be summarized with baseline mean, visit mean, mean change from baseline, mean percentage change from baseline, standard deviation, and the corresponding 95% CIs.

Baseline measurement related to each efficacy endpoint for analysis has been described in Section 7.0.

[figure not shown]
The post-study treatment refers to Post Study Drug Systemic Therapies for Myelofibrosis, Post Study Drug Radiation Therapy and Post Study Drug Transplant. The disease progression (DP) refers to relapse or progressive disease in the Disease Response Assessment Form.

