#### 8.4.1.2 Anemia Response

Anemia response rate is defined as the proportion of subjects who achieved anemia response.

Baseline hemoglobin mentioned below is defined in Section 7.2.2. The transfusion dependency status (transfusion independent and transfusion dependent) mentioned below

are based on investigators reporting in the Study Cancer History Form according PRBC transfusion events ( $\geq 6$  units within 12 weeks and  $\geq 1$  unit within 28 days) prior to the start of study treatment.

For a subject who is transfusion independent (TI) at baseline with hemoglobin value < 10 g/dL, the subject will be considered as achieving anemia response if the post baseline hemoglobin level increases by  $\ge 2 \text{ g/dL}$  from baseline without receiving PRBC transfusion (for any reason) within 2 weeks and without any erythropoietin, erythropoietin mimetics within the last 4 weeks prior to the increase in hemoglobin level by  $\ge 2 \text{g/dL}$  was observed. Hemoglobin values after 30 days post last date of study treatment, the start of post-study treatment or disease progression whichever is earlier will not be considered in the analysis of anemia response.

For a subject who is transfusion dependent (TD) at baseline, anemia response is defined as a period of at least 12 consecutive weeks without PRBC transfusion after the first dose of study drug and on or prior to 30 days post last dose of study drug, the start of post-study treatment, disease progression or death, whichever occurs earlier.

[figure not shown]
Subjects who are baseline transfusion independent with baseline hemoglobin of  $\geq 10$  g/dL will not be included in the analysis since these subjects are not evaluable for anemia response.

Anemia response rate will also be summarized for all subjects who are evaluable for anemia response in the Full Analysis Set and by transfusion dependency status at baseline.

Missing post-baseline anemia response in Full Analysis Set applicable to evaluation of anemia response are considered as non-responders of anemia response.

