#### 8.5.1.7 Duration of Anemia Response

Duration of anemia response will be summarized by baseline transfusion status.

For subjects who were transfusion independent at baseline and achieved anemia response, the evaluation period for duration of anemia response is from achieving anemia response to 30 days after last dose of study treatment. Duration of anemia response is defined as number of days from the first date of achieving anemia response described in Table 6 to the date of loss anemia response as described in Table 7.

Table 6. Date of First Anemia Response for Duration of Anemia Response

Transfusion Status at baseline	Date of First Response
TI	On the first date observing hemoglobin level increase by $\geq 2$ g/dL from baseline without receiving PRBC transfusion within the last 2 weeks or any erythropoietin, erythropoietin mimetics within 4 weeks prior to the increased hemoglobin level
TD	On the first date observing no PRBC transfusion for at least 12 weeks

Table 7. Event and Censoring Condition for Duration of Anemia Response

[figure not shown]
Transfusion Status at baseline	Event/Censor	Date of Event/Censor
TI	Event: 1) decrease in hemoglobin level by 2 g/dL or more from the hemoglobin level at the first occurrence of achieving anemia response, or 2) need for PRBC transfusion before disease progression for the bleeding event* which was unrelated to navitoclax/ruxolitinib or 3) use of any erythropoietin, erythropoietin mimetics within 30 days of last dose of study drug	Earliest date of events
	Censor: if no above-mentioned events observed within 30 days of last dose of study drug	The last date of hemoglobin assessment after achieving anemia response, 30 days post last dose of study treatment, start of post-study treatment, disease progression, or death, whichever is earlier.  Date of achieving anemia response will be the censor date if no hemoglobin assessment is obtained after achieving anemia response.

\* Bleeding event is defined as a treatment emergent hemorrhage event from narrow search of Standardized MedDRA Queries (SMQ). PRBC occurring between the start of bleeding event and end/ongoing will be considered as need for PRBC transfusion for bleeding.

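### The red-cell transfusion evaluation period in SAP 8.5.1.6 does not stop at death or at the last known transfusion status, so up to 30 unobserved days can count as transfusion-free

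*SAP*

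**What the plan says.** SAP 8.5.1.6 defines transfusion independence as "a period of at least 12 weeks (≥ 84 days) with no PRBC transfusions during the evaluation period". The evaluation period starts after the first dose and runs "to earliest day of on or before the last dose of study drug + 30 days, or the start of post-study treatment". The transfusion-independence rate, the conversion rate from dependent to independent, and the duration of independence all rest on this definition.

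Two neighbouring rules end differently:

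- SAP 8.4.1.2 uses the same 12-week criterion for the secondary anemia response in transfusion-dependent subjects. It ends the period at "30 days post last dose of study drug, the start of post-study treatment, disease progression or death, whichever occurs earlier".
- SAP 8.5.1.7, Table 7, covers duration of anemia response in transfusion-independent subjects. It censors at the last hemoglobin assessment or at "30 days post last dose of study treatment, start of post-study treatment, disease progression, or death, whichever is earlier".

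The protocol plans to observe the 30 days after treatment. Section 5.1 states: "All subjects will have one Safety Follow-up visit approximately 30 days following TCV". In Appendix C, Table 6, the row "Transfusion history/status" is marked at the treatment completion visit and at the 30-day safety visit. Section 5.4.1 accepts that some subjects will refuse or be unable to attend that visit and asks only for a source note. Section 8.3.2.4 gives deaths off treatment within 30 days of last dose a reporting category of their own.

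On data cutoff, SAP 8.1 says only that "data collected after the cutoff date will be excluded from statistical analysis". It does not shorten any evaluation period.

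**The concern.** Independence is scored from the absence of a recorded transfusion. If the period continues after a subject has died or left observation, no transfusion can be recorded in the remaining days, and as written they lengthen the transfusion-free run.

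The effect on the rates has one direction. Extra days can turn a failure into a success but never the reverse, and the subjects who gain are those who died or left early. It can also make two tables of the same report disagree about one subject, because the conversion rate (8.5.1.6) and the transfusion-dependent anemia response (8.4.1.2) share the 12-week criterion but not the end rule.

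**Working it through.** **Plan's own figure.** 12 weeks × 7 = 84 days, as SAP 8.5.1.6 states.

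**Inputs.** Threshold of 84 days and tail of 30 days (SAP 8.5.1.6). Planned cohort sizes of 34, 80, 30 and 30 (SAP 2.2). Let g be the days from last dose to death or last known transfusion status, and s the days from last dose to post-study treatment, if any.

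**Formulas.**

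- Tail credited by the rule = min(30, s), or 30 if no post-study treatment starts.
- Unobserved days credited = that tail − g, when positive.
- Observed run that suffices = 84 − unobserved days credited.

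**No post-study treatment:**

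| g (days) | Unobserved days credited | Observed run that suffices |
|---|---|---|
| 0 | 30 | 54 |
| 10 | 20 | 64 |
| 20 | 10 | 74 |
| 29 | 1 | 83 |
| 30 | 0 | 84 |

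At worst, 30/84 = 36% of the required time is unobserved. If post-study treatment starts 0, 7 or 14 days after last dose, the whole tail is only 0, 7 or 14 days.

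**Death example (transfusion-dependent at baseline).** Last PRBC Day 5, last dose Day 60, death Day 62, no post-study treatment or progression.

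- 8.5.1.6: the period ends on Day 60 + 30 = 90. The run is Days 6–90, or 90 − 5 = 85 days. This is ≥ 84, so the subject counts as converted.
- 8.4.1.2: the period ends at death. The run is Days 6–62, or 62 − 5 = 57 days. This is < 84, so the subject is a non-responder.

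**Withdrawal example.** Last PRBC Day 30; last dose and last contact Day 84; no death, progression or post-study treatment recorded.

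- Both rules run to Day 84 + 30 = 114. The run is Days 31–114, or 114 − 30 = 84 days, which meets the criterion.
- Observed: Days 31–84, or 84 − 30 = 54 days.

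Here 8.4.1.2 gives the same wrong answer, because it has no last-contact end point either.

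**Never-transfused subject who dies on the day of last dose (period counted from Day 2).** As written, a last dose on Day 55 suffices, since Days 2–85 are 84 days. With the period stopped at death, the last dose would have to fall on Day 85 or later.

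**Size per subject, full cohort denominator.** 1/34 = 2.94 points in Cohort 1a, 1/80 = 1.25 in Cohort 1b and 1/30 = 3.33 in Cohort 2 or 3. If the conversion rate is taken over the m subjects who were dependent at baseline, one subject adds 100/m points. The documents do not give m; for assumed values of 5, 8 and 15 this is 20, 12.5 and 6.7 points.

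**Duration.** A qualifying run that lasts to the end of the period can be overstated by the unobserved credit, at most 30 days.

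**The case against.** The strongest reply is that the tail is observed by design. Every subject is scheduled for a safety visit at which transfusion status is taken, and Protocol 5.3.1.1 allows it to be collected by phone or virtually during the pandemic. This stands and limits the point to subjects who die, withdraw, are lost or miss that visit. A reader might infer that every subject receives 30 unobserved days; the documents do not support that, and post-study treatment can also end the period sooner.

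A second reply is that no sentence says unobserved time counts as transfusion-free, that SAP 8.2 treats subjects without response as non-responders, and that SAP 1.0 leaves programming detail to a separate programming plan that is not supplied. The wording of the end rule is also awkward, and a programmer might stop at the last record. But no last-record rule is written. SAP 8.2 does not help either: under the 8.5.1.6 definition as it stands, the subject in the death example does have a response.

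A third reply is that the secondary endpoint already stops at death and progression. That is correct, so the death example cannot affect it.

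A fourth is that the two measures may legitimately differ on disease progression. This also stands. Protocol 5.4.1 ties withdrawal at progression to the investigator's view that benefit has ended, so transfusion data can exist after progression. Whether to use them is a choice of what to estimate.

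**Conclusion.** The point holds for a limited group. SAP 8.5.1.6 omits death and last known transfusion status as end points, and its literal application gives a wrong result in cases the protocol itself foresees. The error can only raise the exploratory independence and conversion rates, by the per-subject amounts above, and lengthen individual durations by up to 30 days. How many subjects are affected cannot be derived from the documents.

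A false call needs all of the following:

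- observation ends before last dose + 30 days;
- no post-study treatment cuts the period before the run reaches 84 days;
- the final observed run lies between the sufficient length in the table and 83 days (54 to 83 when observation ends on the day of last dose);
- there is no earlier run of 84 days.

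A reader might infer that any subject with 54 to 83 transfusion-free days at last dose becomes a success. That goes too far, because it ignores the second and fourth conditions and the dependence on when observation ends.

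The primary endpoint is unaffected. The secondary anemia response in transfusion-dependent subjects is exposed only through last contact and data cutoff. The cutoff part is conditional. SAP 11.0 analyses each cohort once it completes Week 24 and adds summaries from the others, so subjects may still be on treatment. Their period runs past the cutoff only if the latest recorded dose is taken as last dose, which the SAP does not specify.

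**What to change.** In SAP 8.5.1.6, end the evaluation period at the earliest of last dose + 30 days, start of post-study treatment, death, last date with known transfusion status, and data cutoff. Require all 84 days to lie inside that period, and measure duration within it.

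In the transfusion-dependent paragraph of SAP 8.4.1.2, add last date with known transfusion status and data cutoff to the existing list.

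Define last known status as the latest contact at which transfusion history was taken, so that a completed 30-day safety visit still covers the tail. Ending 8.5.1.6 at disease progression is optional and not part of the correction; if the two sections are to differ there, say so.

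The cost is a sentence in each section and one derivation line, with no new data collection. The rates become slightly less favourable, and a subject whose run is still short of 84 days at a cutoff counts as a failure until later data are included.

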# 4.0 Analysis Populations

[figure not shown]
In this study, study treatment is navitoclax + ruxolitinib (Cohort 1a, 1b and 3) or navitoclax alone (Cohort 2). Unless otherwise noted, study drug refers to navitoclax and ruxolitinib for combination therapy (Cohort 1a, 1b, and 3); and navitoclax for mono therapy (Cohort 2). Cohort 1 refers to Cohort 1a and Cohort 1b together.

The following sets will be used for analyses:

Full Analysis Set (FAS) includes all enrolled subjects who received at least one dose of navitoclax. The FAS will be used for all demographic/baseline analyses. Unless otherwise specified, the FAS is also the analysis population for the primary and the secondary endpoints.

The Safety Analysis Set includes all enrolled subjects who received at least one dose of navitoclax. The safety analysis set will be used for all safety analyses, unless otherwise specified.

The pharmacokinetics (PK) analysis set includes all the enrolled subjects who received at least one dose of navitoclax and have at least one post-dose PK assay results. The PK set will be used for PK analyses.

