- \* Increase in severity of anemia constitutes the occurrence of new transfusion dependency or a ≥ 2 g/dL decrease in Hgb from pretreatment baseline that lasts for ≥ 12 weeks. Increase in severity of thrombocytopenia or neutropenia is defined as a 2-grade decline, from pretreatment baseline, in platelet count or ANC. In addition, assignment to Clinical Improvement requires a minimum platelet count of ≥ 25 × 10^9/L and ANC ≥ 0.5 × 10^9/L.
- \*\* Transfusion dependency before study enrollment is defined as transfusions of at least 6 units of packed red blood cells (PRBC), in the 12 weeks prior to study enrollment. In addition, the most recent transfusion episode must have occurred in the 28 days prior to study enrollment. Response in transfusion-dependent patients requires absence of any PRBC transfusions during any consecutive "rolling" 12-week interval during the treatment phase.
- \*\*\* Requires confirmation by MRI with a  $\geq$  35% SVR.

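### The exploratory transfusion-independence rate in SAP 8.5.1.6 pools both baseline transfusion statuses and keeps later-dependent subjects as successes, and no analysis reports the independent-to-dependent proportion

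*SAP*

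**What the plan says.** SAP 8.5.1.6 defines an exploratory rate: "Post baseline transfusion independent rate will be calculated as the proportion of subjects who achieved PRBC transfusion independent during the treatment period". Independence means a period of at least 12 weeks (84 days) "with no PRBC transfusions during the evaluation period". The "evaluation period is from after the first dose of study drug to earliest day of on or before the last dose of study drug" plus 30 days, or to the start of post-study treatment if that is earlier. Unlike the anemia-response window in SAP 8.4.1.2, it does not stop at disease progression.

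On the denominator: "Above endpoints will be analyzed in the Full Analysis Set". SAP 4.0 says the "Full Analysis Set (FAS) includes all enrolled subjects who received at least one dose of navitoclax"; it sets no transfusion criterion. SAP 8.1 presents efficacy results by cohort, so the pooling is within each cohort.

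The section adds one directional rate: "the rate of conversion will be calculated as proportion of subjects being post-baseline PRBC transfusion independent from baseline PRBC transfusion dependent". It also plans the duration of the first qualifying period (overall and by baseline status), PRBC incidence per subject-month, and time to the first 2 or more units. SAP 9.2.5.3 counts subjects who receive at least 2 units of PRBC in total.

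In SAP Appendix B, a footnote to the Clinical Improvement category says: "Increase in severity of anemia constitutes the occurrence of new transfusion dependency", or a sustained hemoglobin fall.

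**The concern.** A subject who enters without transfusion dependence has nothing to achieve in the sense that the word suggests, yet enters numerator and denominator on the same terms as a dependent subject. The qualifying period need not be sustained, be the most recent one, or follow dependence. Nothing later in the record can undo it.

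Transfusion burden can move either way in this trial. SAP 3.4 lists PRBC transfusion requirement as a safety endpoint. Protocol 5.6.3 gives anemia as one of the primary reasons for ruxolitinib dose reduction in Cohort 1a. Protocol 5.2.1 (criterion 8c) uses a new transfusion requirement to define ruxolitinib intolerance for Cohort 1b. A rate called transfusion independent, accompanied only by the favourable conversion, invites a reader to take it as improvement and gives no matching figure for deterioration.

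**Working it through.** **No plan figure to reproduce.** Neither document gives an expected rate, precision or sample size for this endpoint. The check is a test of the definition on one constructed subject, then an illustration with assumed inputs.

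**Step 1: one timeline.** A baseline-independent subject receives no PRBC on Days 2 to 85, which is 85 - 2 + 1 = 84 days. The subject then receives 2 units on Days 86, 100, 114, 128, 142 and 156.

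- SAP 8.5.1.6: 84 free days, so the subject counts as a success.
- Units in the 84 days ending on Day 168: 6 × 2 = 12. Last transfusion: 168 - 156 = 12 days earlier.
- Baseline dependence definition (SAP 8.4.1.2 and Appendix B): at least 6 units in 12 weeks, with the most recent transfusion within 28 days. Both thresholds are met.

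The same subject is a success under the rate and dependent under the plan's thresholds. Also, because the window runs 30 days past the last dose, a last dose on Day 55 is enough to qualify (55 + 30 = 85).

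**Step 2: what the companion analyses show for this subject.**

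| Analysis | Shows | Does not show |
|---|---|---|
| Conversion rate (8.5.1.6) | Dependent to independent | The reverse shift |
| Duration by baseline status (8.5.1.6) | About 12 weeks, in the independent row | What followed the first period |
| PRBC incidence per subject-month (8.5.1.6) | Added transfusions | Who received them, or their baseline status |
| Time to first 2 or more units (8.5.1.6) | Day 86 | Isolated episode or new dependence |
| Subjects with at least 2 units (9.2.5.3) | Counted once | Isolated episode or new dependence |

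None yields the proportion of baseline-independent subjects who become dependent.

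**Step 3: size, with assumed inputs.** N = 80 is the planned size of Cohort 1b. Everything else is assumed: 10%, 20% or 40% dependent at baseline; 0% or 20% of those converting; 70% or 90% of independent subjects having an 84-day run; 10% or 30% of independent subjects becoming dependent after such a run. Counts are rounded to whole subjects.

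- Rate as written = (converters + independent subjects with a run) / N
- Rate without later-dependent subjects = (the same numerator - later-dependent subjects) / N
- Gap = later-dependent subjects / N

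*One case.* 16 dependent, 64 independent, no converters, 58 of 64 with a run, 19 later dependent:

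- as written, 58/80 = 72.5% (Clopper-Pearson 95% CI 61.4 to 81.9), whether or not the 19 deteriorate
- without them, (58 - 19)/80 = 39/80 = 48.8%

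*Ends of the grid.*

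- Smallest gap: 48 independent, 10% later dependent, 5 subjects, 5/80 = 6.25 points.
- Largest gap: 72 independent, 30% later dependent, 22 subjects, 22/80 = 27.5 points.
- Rate as written: lowest (0 + 34)/80 = 42.5%, highest (2 + 65)/80 = 83.8%.

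**The case against.** The strongest reply is that the item is minor and partly covered. It is exploratory, no test or sample size rests on it, and the conversion rate already isolates improvement among dependent subjects. The secondary anemia-response endpoint (SAP 8.4.1.2) does not share the flaw: it excludes independent subjects with hemoglobin of at least 10 g/dL, requires a 2 g/dL rise in the other independent subjects, and is summarised by baseline status. Duration, incidence, hemoglobin grade shifts and adverse-event tables would all register worsening anemia. This stands, and it limits the weight of the point. It does not supply the missing proportion.

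Four stronger readings are tempting, and the documents do not support them.

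- *The rate can hardly fall, or only mirrors the baseline mix.* A subject transfused regularly from the start, or followed for under 84 days, fails. The illustrated rate runs from 42.5% to 83.8%.
- *The distortion is a third of the cohort or more.* With 85% independent at baseline, all of them completing a run and 40% later dependent, the gap is 0.85 × 0.40 = 34 points. The documents support none of these inputs, and complete attainment of an 84-day run is unlikely to hold.
- *Every baseline-independent success is empty.* Independence here appears to mean not meeting the 6-unit definition, so it can include subjects with 1 to 5 units in the prior 12 weeks. For them 84 free days may be real benefit.
- *SAP 8.5.1.6 contradicts Appendix B.* The Appendix B footnote qualifies Clinical Improvement only, and the unit threshold is written for the period before enrolment: "Transfusion dependency before study enrollment is defined as transfusions of at least 6 units of packed red blood cells (PRBC), in the 12 weeks". Using it on treatment is an extension, not an existing rule that has been broken.

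**Conclusion.** The point holds as a gap in an exploratory analysis. Within each cohort's FAS, the rate pools two populations for whom the result means different things, and later dependence cannot remove a success. The favourable shift has its own rate; the unfavourable shift has none. The reading of the definition is firm.

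The size is not firm. The range of about 6 to 28 points rests wholly on the assumed baseline mix and worsening rates, and on every later-dependent subject having first had an 84-day run.

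A reader might infer that repairing the table would show whether the regimen causes transfusion dependence. It would not: the study is open-label and non-randomized (SAP 2.3), so the shift would remain descriptive. Nor does the point touch the primary or secondary endpoints. It is a cheap improvement.

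**What to change.** In SAP 8.5.1.6:

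1. Report the rate separately by baseline transfusion status within each cohort. Use the word achieved only for baseline-dependent subjects, where it is the existing conversion rate. Label the other row as having at least one 84-day PRBC-free period.
2. Add a two-way shift table of baseline status against status on treatment. Include the proportion of baseline-independent subjects who meet the baseline dependence definition on treatment: at least 6 units in a rolling 12-week window, with the latest transfusion within 28 days. State that this extends the pre-enrolment definition in SAP 8.4.1.2 and Appendix B. Also state that it is derived from transfusion records, because baseline status is investigator-reported.
3. Use the existing SAP 8.5.1.6 evaluation period, and show how many subjects in each row have less than 84 days of evaluation.

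No new data are needed: transfusion status is collected at the scheduled treatment visits (Protocol Appendix C, Table 6), and the SAP already uses units and baseline status. The cost is SAP wording, one extra table and a less favourable exploratory rate.
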